#### **1.5 Clinical Experience with SYN023**

SYN023 administration exhibited an acceptable safety profile in protocol SYN023-001. There were no SAEs or acute allergic reactions and local toxicity was mild. SYN023 antibody concentrations are pending for Study SYN023-001, however RVNA determinations are final. All five subjects in each dose group of protocol SYN023-100 lacked RVNA prior to SYN023 injection and exhibited measurable RVNA after administration thus, it is reasonable to conclude that the RVNA was the result of SYN023 antibody injection. If this is true then the two higher doses of 1.0 mg/kg and 3.0 mg/kg exceeded rabies virus neutralizing activity for 84 days and the mean level of the lowest dose of SYN023 tested in Protocol SYN023-001 (0.3 mg/kg) exceeded rabies virus neutralizing activity ( $\geq 0.5$  IU/mL) by over five-fold in the serum for at least 28 days (Table 1.5-1). The descriptive statistics including mean, standard error and 95% confidence intervals were calculated by SAS 9.4 (Cary, NC, USA) and figure 1.5-1 was generated using Graphpad Prism 5.0 (San Diego, CA, USA)

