### Criteria for Pharmacodynamic Similarity Acceptance

Rabies Virus Neutralizing Activity plotted against time will be created. Pharmacodynamic parameters for SYN023 mAb will be estimated using non-compartmental analysis. Cmax, Tmax, AUC0-last, AUC0-inf will be calculated. For the comparison of RIG to SYN023 with RVi and RVa vaccines: The 90% confidence intervals for the ratio of geometric means (RIG/SYN023) must be 80% to 125%. An ANOVA of the ln-transformed AUC0-inf will be run to determine the 90% confidence interval on the difference between treatments. The confidence interval limits derived on the log scale will be back-transformed to the raw AUC scale for comparison to the acceptance criteria.

To investigate any interference of SYN023 to the immune response generated by the vaccine, a non-inferiority test of the AUC14-last between RIG and SYN023 for each vaccine can be performed. The one-sided 90% confidence interval derived on the log transformed AUC from an ANOVA would be compared to the lower acceptance criterion of 80%.

Additionally, a non-inferiority test of the level of RVNA between RIG and SYN023 for each vaccine at selected time points, such as 14 or 28 days, can be performed using a Wilcoxon rank sum approach with a non-inferiority of 10% of the level associated with RIG. Pharmacodynamic efficacy will be defined as RVNA measured above 0.5 IU/mL with RVi and RVa for the duration of the trial and no more than 10% lower for SYN023 compared to RIG at any time point through Study Day 35.

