### **7.7 Sample Size Considerations**

The sample size for this Phase 2 study was selected based on requirement to consider noninferiority of the efficacy parameter, RVNA. The power analysis was performed in SAS 9.2 using the power procedure for noninferiority testing under the assumption of the sample size of 40 per group and likely margin corresponding to SYN023 being no less than 10% lower than RIG. Based on earlier studies, the mean RVNA for 0.3 mg/kg SYN023 of 20 with CV of 15-25% are reasonable. For assumed underlying differences of 0 to 1 IU/mL, there is over 80% to conclude non-inferiority of RVNA level at a specified time point. The sample size of 40 per treatment group should be sufficient to address the efficacy objectives of the study.

The assumptions that a difference of 2 or less is considered unimportant (the approximate mean value for 0.3mg/kg SYN023 of 20 was used), with the range in mean difference from -1 to 1, standard deviation of 3 and power of 0.8, the required sample size of 29 is needed to declare that the new treatment (SYN023) is not more tolerably inferior to the previous treatment (RIG). Also, the power analysis was performed for the sample size of 40, standard deviation 3 and the mean difference of 2. This resulted in the power of 0.838. The above results from the sample size and power analysis showed that the sample size of 40 should be sufficiently powered for this study.

Also, a power analysis for non-inferiority of the AUCs was performed using “PowerTOST”, an R CRAN package run under Rstudio version 0.99.491. Under the assumption of a lower non-inferiority bound of 0.9 (corresponding to SYN023 being no less than 10% lower than RIG), the selected sample size of 40 per group would provide over 80% power assuming a CV of 10-20%.

If no SAEs are observed among subjects in each dose group and the 40 subjects in the 3 dose groups combined, the one-sided exact upper 95% confidence bounds on the rate of SAE occurrence will be 45% and 18%, respectively.

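### Section 7.7's claim of over 80% time-point power holds only near the favourable end of its own inputs, and the CV behind it has no traceable source in vaccinated subjects

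*Protocol*

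**What the plan says.** Protocol Section 7.7 gives the inputs for RVNA at a single time point:

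- Mean and spread: "Based on earlier studies, the mean RVNA for 0.3 mg/kg SYN023 of 20 with CV of 15-25% are reasonable".
- Margin: a "likely margin corresponding to SYN023 being no less than 10% lower than RIG". On the absolute scale this is 2 IU/mL: "The assumptions that a difference of 2 or less is considered unimportant".
- Claim: "For assumed underlying differences of 0 to 1 IU/mL, there is over 80% to conclude non-inferiority of RVNA level at a specified time point".
- Worked examples: first "standard deviation of 3 and power of 0.8, the required sample size of 29 is needed". Then, for 40 subjects, an SD of 3 and a difference of 2: "This resulted in the power of 0.838".

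Alpha and sidedness are not stated. The section concludes that 40 per group should be enough for the efficacy objectives.

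Protocol Section 7.3 says a time-point non-inferiority test can be performed for each vaccine at selected days, with 14 and 28 as examples. It also defines pharmacodynamic efficacy as RVNA above 0.5 IU/mL throughout and "no more than 10% lower for SYN023 compared to RIG at any time point through Study Day 35".

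The SAP makes AUEC0-t the primary parameter (Section 5), with a 90% confidence interval for the ratio required to lie within 80-125% (Section 10.4.1). Its time-point comparison (Section 10.4.2) reports ratios with 90% and 95% intervals and sets no 10% margin.

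**The concern.** When the margin is 10% of the mean, power depends almost entirely on the CV and on how much of the margin the true difference uses up. Both worked examples sit at an SD of 3, which is 15% of 20 and so the lowest CV in the stated range. The over-80% statement reads as if it covered the whole range of CVs and differences.

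The CV is attributed to unnamed earlier studies. The only human RVNA data in either document are in Table 1.5-1, from the Phase 1 study of SYN023 without vaccine, with five subjects per dose. This trial measures RVNA in subjects who also receive five vaccine doses, and no mean or CV is given for that setting.

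If the power is overstated, a time-point comparison that misses the 10% limit could be read as interference with the vaccine when it reflects low power.

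**Working it through.** **Inputs (Section 7.7).** n = 40 per group; mean 20; margin 2; CV 15-25%, so SD = 20 × CV = 3 to 5. *d* is the true amount by which SYN023 is lower than RIG. A two-sample t-test is assumed; alpha is assumed at one-sided 5% and 2.5%.

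**Formula.** Power = P(T > t₁₋α with 78 df), where T is noncentral t with noncentrality (2 − d) / (SD × √(2/40)), and √(2/40) = 0.2236.

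**The plan's own figures.**
- 0.838: SD 3, d = 0 gives noncentrality 2/0.671 = 2.98 and power 0.838 at one-sided 2.5% (0.905 at 5%). It reproduces if the stated difference of 2 is the distance to the margin.
- n = 29: reproduces at SD 3, d = 0, one-sided 5% (power 0.806 at 29 and 0.793 at 28). At one-sided 2.5% the answer is 37.

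So the two examples use different alphas, and both reproduce at a CV of 15% with zero true difference.

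**Over the stated range, 40 per group:**

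| CV | d = 0: one-sided 5% / 2.5% | SYN023 lower by 1: 5% / 2.5% |
|---|---|---|
| 15% | 0.91 / 0.84 | 0.43 / 0.31 |
| 20% | 0.72 / 0.60 | 0.30 / 0.20 |
| 25% | 0.55 / 0.42 | 0.22 / 0.14 |

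For example, at CV 25% and d = 0 the noncentrality is 2/(5 × 0.2236) = 1.79; at CV 15% and d = 1 it is 1/(3 × 0.2236) = 1.49.

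**Highest CV giving 80% power (5% / 2.5%).** d = 0: 17.8% / 15.8%. SYN023 lower by 1: 8.9% / 7.9%, below the stated range.

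**Variants.** Log scale with a bound of 0.9, CV 25%, true ratio 1: 0.60 / 0.47. One-sided 10%, d = 0: 0.83 at CV 20% and 0.69 at CV 25%.

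**Where the CV might come from.** Table 1.5-1 does not define its ±. For 0.3 mg/kg, reading ± as an SD (CV = ± / mean):

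| Day | 1 | 3 | 7 | 14 | 28 | 35 |
|---|---|---|---|---|---|---|
| Mean ± | 2.70 ± 0.43 | 3.68 ± 0.56 | 4.44 ± 1.09 | 3.78 ± 0.41 | 2.82 ± 0.61 | 1.82 ± 0.93 |
| CV | 15.9% | 15.2% | 24.5% | 10.8% | 21.6% | 51.1% |

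If ± is a 95% half-width, SD = ± × √5 / 2.776 (t) or / 1.96 (z), and the Day 35 CV is 41% or 58%. Section 1.5 says "The descriptive statistics including mean, standard error and 95% confidence intervals were calculated by SAS 9.4", but ± cannot be a standard error: for five non-negative values the standard error cannot exceed the mean, and Day 84 is printed as 0.22 ± 0.25.

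**The SAP's formal criterion.** For AUEC0-t within 80-125%, with a 90% interval, true ratio 1 and log-scale SD = √ln(1 + CV²), power is about 0.80 at a CV of 35% for one vaccine (40 vs 40) and at a CV of 51% with vaccines pooled (80 vs 80).

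**The case against.** Four points can be made for the plan.

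1. *The direction of the 0 to 1 difference is not stated.* If it favours SYN023, power at a CV of 25% is 0.85 / 0.76. This stands for that case, but zero difference is also in the stated range and gives 0.55 / 0.42.
2. *The vaccines could be pooled, as the SAP does when the interaction is not significant.* With 80 per arm, CV 25% and zero difference, power is 0.81 at one-sided 5%, so the claim just holds there. It is 0.71 at 2.5%, and 0.35 / 0.24 with SYN023 lower by 1. Section 7.7 claims its power for 40 per group, and Section 7.3 describes the test for each vaccine.
3. *The claim concerns one specified time point, and the test is optional.* Both are true. Section 7.7 does not claim power for every day through Day 35.
4. *The formal criterion lies elsewhere.* The SAP judges similarity on AUEC0-t and sets no 10% time-point margin. This limits the consequence considerably.

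Two stronger readings are tempting. A reader might infer that the 15-25% was taken from the favourable days of Table 1.5-1, leaving out Day 35. The documents do not show this: the mean of 20 is not in the 0.3 mg/kg row, whose highest mean is 4.44; Day 14 falls below the range at 10.8%; and the match needs ± to be an SD.

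A reader might also put the Day 35 CV of 41-58% into the formula (power 0.19 to 0.29 at one-sided 5%, zero difference) and take that as the trial's Day 35 power. That does not follow either. The Phase 1 value describes waning SYN023 around a mean of 1.82, in five subjects, whereas Day 35 here comes after all five vaccine doses.

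**Conclusion.** The over-80% claim in Section 7.7 is not supported across its own inputs. At 40 per group it holds with zero true difference only up to a CV of about 17.8% (one-sided 5%) or 15.8% (2.5%). At the top of the stated range power is 0.55 / 0.42. If SYN023 is truly lower by 1 IU/mL, power is at most 0.43 / 0.31 anywhere in the range. These results assume a two-sample t-test, a fixed margin of 2 IU/mL and the alphas shown, since the protocol states none.

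Separately, neither the mean of 20 nor the CV can be traced to vaccinated subjects. The Table 1.5-1 Day 35 spread, on a day inside the protocol's 10% limit, shows that the input is uncertain; it does not estimate this trial's CV.

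This does not show that the trial is underpowered for its formal AUEC0-t comparison. The stated time-point power should be corrected, but the sample size need not be reopened on this ground.

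**What to change.** In Protocol Section 7.7:

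- Replace the single power statement with a small table by CV (15%, 20%, 25% and a wider sensitivity range, for example to 60%) and by true difference with its direction. State alpha, sidedness and whether the comparison is per vaccine or pooled. Limit the 80% claim to the cells where it holds.
- Name the source of the mean of 20 and the CV of 15-25%, or state that they are assumptions not drawn from vaccinated subjects.
- State that the SAP's AUEC0-t 80-125% criterion keeps about 80% power at a true ratio of 1 up to a CV of about 51% pooled (80 vs 80) or 35% per vaccine (40 vs 40), so that the observed log-scale CV can be compared with it in the report.

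In Table 1.5-1, label the ±.

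The cost is wording and one table, with no extra subjects. The downside is a less favourable stated power for the time-point comparison.

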**Table 1.5-1 Mean RVNA activity in IU by dose level in Phase I study of SYN023. Five subjects in each group.**

Dose Level mg/kg	Study Day							
	0	1	3	7	14	28	35	84
0.3	0.00 ± 0.00	2.70 ± 0.43	3.68 ± 0.56	4.44 ± 1.09	3.78 ± 0.41	2.82 ± 0.61	1.82 ± 0.93	0.22 ± 0.25
1.0	0.00 ± 0.00	8.88 ± 3.13	10.02 ± 2.07	17.00 ± 8.81	11.2 ± 3.24	10.3 ± 3.37	11.64 ± 3.86	2.22 ± 1.06
2.0	0.02 ± 0.00	13.40 ± 8.19	27.60 ± 3.31	35.00 ± 2.40	35.6 ± 3.85	13.80 ± 7.61	10.14 ± 2.12	3.76 ± 1.07

These results are graphically presented for the lowest dose group as means ± 95% confidence interval (Figure 1.5-1). Rabies neutralizing activity from IM injection Study Day 0 was measurable and several-fold above the minimum inhibitory level of 0.5 IU/mL on Study Days 1, 3, 7, 14 and 28.

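### Protocol 7.7 overstates its time-point power: over 80% does not hold across its own inputs even at zero difference, n = 29 and 0.838 imply different alphas, and the zero-SAE bounds are those for 5 and 15 subjects

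*Protocol*

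**What the plan says.** Protocol 7.7 bases the sample size on RVNA non-inferiority. The inputs are a "sample size of 40 per group and likely margin corresponding to SYN023 being no less than 10% lower than RIG" and the statement that "the mean RVNA for 0.3 mg/kg SYN023 of 20 with CV of 15-25% are reasonable". The conclusion is: "For assumed underlying differences of 0 to 1 IU/mL, there is over 80% to conclude non-inferiority of RVNA level at a specified time point". The next paragraph treats a difference of 2 or less as unimportant, which is 10% of 20.

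Two calculations are offered in support. One reads "with the range in mean difference from -1 to 1, standard deviation of 3 and power of 0.8, the required sample size of 29". The other was run "for the sample size of 40, standard deviation 3 and the mean difference of 2. This resulted in the power of 0.838". No alpha is given for either, and no direction is given for the difference.

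On safety precision the section sets out two cases without events: "If no SAEs are observed among subjects in each dose group and the 40 subjects in the 3 dose groups combined". The trial, however, has four arms of 40 (Protocol 2.2, Table 2.2-1). For these two cases 7.7 reports that "the one-sided exact upper 95% confidence bounds on the rate of SAE occurrence will be 45% and 18%, respectively".

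A further paragraph of 7.7 claims over 80% power for AUC non-inferiority with 40 per group, a bound of 0.9 and CV 10-20%.

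**The concern.** The power statement covers a range of CVs and differences, but both supporting calculations use SD 3, which is CV 15% and the most favourable end of that range. With the margin fixed at 2 IU/mL, raising the SD to 5 or using up half the margin with a true deficit of 1 should cut power sharply.

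Separately, a zero-event upper bound of 45% is far too wide for an arm of 40, and the sentence counts three dose groups where the trial has four arms.

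At stake is the reliability of the planning statement. A reader who trusts it could take a failed 10% comparison at one time point as evidence of a SYN023 deficit when low power would explain it equally well, and would think the trial much less informative about SAEs than it is.

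**Working it through.** **Inputs (Protocol 7.7).** n = 40 per group; mean 20; CV 15/20/25%, so SD 3/4/5; margin 2; true difference d (SYN023 minus RIG) of 0, -1 or +1. Protocol 7.3 makes the comparison within each vaccine, hence 40 v 40. Alpha is unstated, so one-sided 2.5, 5 and 10% are shown.

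**Formula.** Non-inferiority t-test: SE = SD × √(2/n), noncentrality = (2 + d)/SE, power = P(noncentral t > critical t), df = 2n - 2. This is a raw-scale proxy for the Wilcoxon test of Protocol 7.3 and the ln-scale ANOVA of SAP 10.4.2.

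**Reproducing the plan's own figures.**
- 0.838: n = 40, SD 3, d = 0 gives SE = 3 × √(2/40) = 0.671 and noncentrality 2/0.671 = 2.98. At one-sided 2.5% the power is 0.8376, which matches. An ordinary two-sided 5% difference test for a true difference of 2 gives the same number. A true SYN023 deficit of 2 sits on the margin, where non-inferiority power equals alpha, 2.5%.
- n = 29: SD 3, d = 0, one-sided 5% gives 80.6%, which matches; one-sided 2.5% would need 37. With n = 29 at one-sided 5%, d = +1 gives 98.3% and d = -1 gives 34.8%. Reaching 80% at d = -1 takes 112 per group.

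**Power over the stated range**, in % at one-sided 2.5 / 5 / 10%:

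| | CV 15% | CV 20% | CV 25% |
|---|---|---|---|
| 40 v 40, d = 0 | 83.8 / 90.5 / 95.4 | 59.8 / 71.6 / 82.7 | 42.3 / 55.1 / 69.1 |
| 40 v 40, d = -1 | 31.3 / 43.4 / 58.0 | 19.6 / 29.6 / 43.3 | 14.1 / 22.4 / 34.8 |
| 40 v 40, d = +1 | 99.3 / 99.7 / 99.9 | 91.2 / 95.4 / 98.0 | 75.5 / 84.5 / 91.7 |
| 80 v 80, d = 0 | 98.7 / 99.5 / 99.8 | 88.2 / 93.4 / 96.9 | 71.0 / 80.9 / 89.3 |
| 80 v 80, d = -1 | 55.4 / 67.5 / 79.4 | 34.9 / 47.2 / 61.6 | 24.1 / 35.0 / 49.2 |

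The 80 v 80 rows use df 157, for the pooled main-effects model that SAP 10.4.2 fits when the interaction is not significant. At 40 v 40 and d = 0, power reaches 80% only up to CV 15.8/17.8/21.0%.

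**Sensitivity to the proxy (40 v 40).**
- If RIG is 21 and the margin is 10% of that (2.1), the best deficit case is 63.7%.
- On the ln scale (SD = √ln(1 + CV²), bound 0.9), the best case at ratio 0.95 is 63.0%. At ratio 1 and CV 25% the ln scale gives 47.2/60.0/73.3%.
- A simulated Wilcoxon test (20,000 trials, normal data) at d = 0, CV 25%, one-sided 5% gives 52.7%.

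**SAE bounds.** With no events the one-sided exact 95% upper bound is 1 - 0.05^(1/n): n = 5 gives 45.1%, n = 15 gives 18.1%, n = 40 gives 7.2%, n = 80 gives 3.7%, n = 160 gives 1.9%. The Phase 1 study in Protocol Table 1.5-1 had three dose levels ("Five subjects in each group"), that is 5 and 3 × 5 = 15.

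**AUC power (secondary).** At bound 0.9, CV 20%, true ratio 1, 40 v 40: 65.2/76.2/86.1%. Pooled 80 v 80: 91.7/95.6/98.1%.

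**The case against.** - *Direction.* The stated difference of 0 to 1 may favour SYN023. If so, power at +1 exceeds 80% in every 40 v 40 cell but one (75.5%). This stands, and it makes the deficit result conditional. It does not rescue zero difference, which lies inside the stated range whichever sign is meant.
- *Pooling.* With 80 v 80, zero difference exceeds 80% at every stated CV at one-sided 5% or 10%. This also stands, but 7.7 computes with 40 per group and 7.3 tests each vaccine separately. A deficit of 1 stays below 80% pooled on the raw scale; the one exception is the ln scale at CV 15%, one-sided 10% (84.3%).
- *Labelling.* Both 0.838 and 29 are correct at SD 3 and zero difference. True: the numbers are not wrong, only their description. The two alphas are inferred by back-solving, not stated.
- *The efficacy definition.* A reader might infer that the 10% criterion defining pharmacodynamic efficacy in Protocol 2.2 and 7.3 lacks its stated power. That definition names no test, interval or alpha, and 7.7 speaks of a test at one specified time point, so the link is an inference.
- *AUC.* A reader might infer that the AUC statement is false. It is not shown to be. At CV 20% and 40 v 40, 80% power is reached at SYN023/RIG ratios of about 0.989, 1.006 and 1.02 at one-sided 10, 5 and 2.5%, and 7.3 uses a one-sided 90% interval for AUC14-last. The claim lacks its conditions.
- *Consequence.* The time-point test is optional in 7.3, SAP 10.4.2 sets no margin, SAP 9 keeps safety descriptive, and the SAE error is conservative. All of this stands.

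**Conclusion.** The concern holds as an error in the planning statement. Over 80% power is not available across the stated inputs. At zero difference and 40 v 40 it fails at CV 25% for all three alphas, and at CV 20% for one-sided 2.5% and 5%. For a SYN023 deficit of 1 it is never reached at 40 v 40: at most 58% with the fixed margin of 2, or about 63-64% with a margin of 2.1 or an ln-scale bound of 0.9. The n = 29 applies only to a zero or favourable difference at SD 3 and one-sided 5%. The 0.838 is non-inferiority power at zero true difference, not at a deficit of 2.

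The SAE bounds do not describe this trial: 45% is about six times the 7.2% that applies to an arm of 40. That they were carried over from Phase 1 is plausible but not documented; the mismatch is arithmetic either way.

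These figures take the mean of 20 and the CV range as given, assume no dropout, and use the t-test proxy; the ln-scale and Wilcoxon checks lead to the same conclusion. A reader might infer that the trial as a whole is underpowered. The documents do not support that: the primary analysis is the 80-125% comparison of AUEC0-t, and nothing here tests its power.

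**What to change.** Correct the text of Protocol 7.7, leaving the sample size and tests unchanged.

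1. Restate the time-point power with one alpha, the sign of the difference and the CV, for 40 v 40 (each vaccine) and 80 v 80 (pooled). Say that it is a raw-scale t-test approximation to the planned Wilcoxon or ln-scale analysis.
2. Limit n = 29 to a zero or favourable difference at SD 3, one-sided 5%. Relabel 0.838 as margin 2, zero true difference, SD 3, one-sided 2.5%. Recompute whichever does not use the alpha chosen in step 1.
3. Replace the SAE sentence with zero-event upper 95% bounds of 7.2% per arm of 40, 3.7% for the 80 SYN023 subjects and 1.9% for all 160.
4. Secondary: state the alpha, true ratio and n behind the AUC power, and reconcile its 0.9 bound with the 80% criterion in 7.3.

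The cost is a wording change. The stated time-point power becomes less favourable at higher CVs or under a SYN023 deficit, and the SAE bounds become tighter.

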## **7.8 Plan for Statistical Summaries and Analyses**

### **7.8.1 Preliminary Data Reviews**

A review of Rabies Virus Inhibitory Activity, anti-SYN023 antibodies, SYN023 pharmacokinetic information and clinical safety data will be conducted following completion of Study Day 42. This review may present individual and aggregate (mean or median [95% CI], as appropriate) and change from pre-study drug to each post administration time point by individual or in aggregate. Study procedures and monitoring practices will not change following this preliminary review. No decision cut points or stopping rules will be stipulated. No hypothesis testing will be performed. The purpose of this review is to obtain preliminary data for use in the decision-making process regarding Study Drug dose level. Personnel at the research site and at the immunology laboratory will remain blinded to all study results and to treatment assignments until after the Study Day 112 data have been collected, reviewed and queries resolved.

### **7.8.2 Final Study Report**

The final study report will include all available safety data, immunogenicity data (including exploratory analyses), clinical assessments, and concomitant medications through the final study visit. The database will be locked prior to preparation of the final study report when all of the above data have been entered, reviewed, and all queries related to the data have been addressed.

Modifications or additions to the analyses described above will be included in the relevant statistical analysis plan(s). Any decisions to deviate from the planned analyses described in the protocol and in the statistical analysis plan will be described in detail in the final study report.

